Moving Mindfully for Freezing in Parkinsons

NCT 05309083

Date 09/19/2022

Moving Mindfully: AIM 1/AIM 2 Protocol/SAP

RESEARCH DESIGN AND METHODS

Aim 1: Create a Mindfulness-Based Walking Therapy (MBWT) program by modifying the MBSR standard protocol based upon feedback from an advisory group. An advisory group consisting of physical therapists, mindfulness instructors, research team members, 3-5 people with PD+FOG and their care partners will provide input regarding adaptations needed to make the standard MBSR program acceptable and feasible for people with PD+FOG and to shift the focus from sitting, standing, or lying meditations to walking mediations.

RATIONALE

The use of an advisory group is a collaborative and valuable research tool that will provide integrated insight to modify the standardized MBSR protocol.

DESIGN

We will recruit 3-5 people with PD+FOG and their care partners and schedule a series of collaborative meetings with team members including the research physical therapist and mindfulness instructors to: 1) modify the MBSR program by replacing sitting, lying, and standing meditations with walking mediations and ensuring the content is appropriate and clear for people who have PD+FOG; and 2) finalize a protocol that will include the MBSR Standards of Practice (SOP). To facilitate these goals, the advisory group will convene once a week for eight weeks that will include discussions about FOG knowledge, existing mindfulness training in PD and older adult literature, inclusion/exclusion criteria, outcome and feasibility measures, and technology usage for tracking adherence. An outline for these objectives is included in the Narrative Study Description.

People with PD+FOG will also be asked to participate in phone interviews to ask questions about their history with FOG and anxiety using questions on the FOG and Anxiety Questionnaire. Information from this interview will provide information about how participants describe and experience FOG and anxiety in their own words and what different scenarios or environments tend to elicit FOG.

A Mindfulness-Based Stress Reduction Workbook. We will use the MBSR Workbook to facilitate the program. The MBSR Workbook follows the teachings and SOP written by Jon Kabat-Zinn and includes both formal and informal practices to better understand and learn mindfulness. There are places to journal, self-reflect, and schedule time to practice mindfulness. Members of the advisory group will receive a copy of the workbook to review for two main purposes: 1) exchange meditations that include sitting, lying, or standing mindfulness practices with walking meditations; and 2) ensure the meditations are appropriate and clear for our population. We will follow the recommendations on how to use the MBSR workbook and include the majority of the current mindfulness practices that are included to ensure adequate mindfulness training. The MBSR Workbook currently includes one walking meditation and the advisory group will create additional walking meditations that address situations that are difficult for people living with PD+FOG. For instance, turning is a frequent occurrence in our daily lives. Additional walking meditations to be proposed will include using mindfulness for complex walking scenarios such as places with large crowds, places that require quick movements such as getting on or off an elevator, walking through narrow spaces and doorways, and surfaces that change (i.e., tile to carpet). Walking mediations that require stopping and starting frequently could address freezing that occurs at gait initiation.

MBSR Standards of Practice (SOP). The MBSR SOP was written by Jon Kabat-Zinn at the Center for Mindfulness in Medicine, Health Care & Society and the University of Massachusetts's Medical School. The SOP includes three main sections that outline the minimum standards required to be considered a MBSR program:

Background and Overview: Presents the fundamental values of MBSR and reflects the methodical, yet flexible, approach of mindfulness training. These values include embracing mindfulness as a positive and educational lifestyle change, incorporating it into daily practice, and the importance of living in the present moment.

Structure and Methods: Presents the outline of successful MBSR programs which includes a pre-program orientation session, eight weekly classes 2.5 hours in duration, an all-day silent retreat during the sixth week of the program (7.5 hours), specified mindfulness mediations methods (i.e., body scan, gentle hatha yoga, sitting mediation, and walking mediation) and practices (e.g., deliberate awareness during routine activities and events such as eating or walking), daily home assignments (e.g., journaling, reading), individual and group dialogue, and exit assessments including a participant self-evaluation. The total in-class contact is 30 hours and total home assignments is a minimum of 42 hours.

Program Standards: The MBSR SOP includes the following pre-program initiatives to ensure participants are familiar with their upcoming involvement. The Program Standards also reviews screening criteria, learning contract, and curriculum guidelines.

Participants are given a Session Evaluation form after each session and the Client Satisfaction Questionnaire (CSQ)⁸³ to complete at the end of the program, both of which provide Likert-scale questions to be used in the feasibility benchmarks and open-ended questions to provide qualitative data to evaluate and refine the meditations, instructions, and study procedures.^{82,84} Insights from these questionnaires and the exit interview will also be used to explore response distributions such as skewness, floor/ceiling effects, or missing data.

The advisory group will be employed to address each of these sections in the MBSR SOP and determine which areas may need modification. Based on our knowledge of working with people with PD+FOG and preliminary studies of MBSR with older adults or people with Parkinson disease, we anticipate changing the all-day silent retreat (7.5 hours) to a half-day retreat (3.5 hours).

Review outcome measures for clarity and burden. We will present the following outcome measures to the advisory group for review.

Functional Measures. The New Freezing of Gait Questionnaire (NFOG-Q) assesses types of freezing and severity for the past month. Represent the StepWatchTM Activity Monitor (SAM)⁸⁷ will be worn on the ankle by participants 24 hours per day for seven consecutive days after each evaluation to record number of daily steps. Motor systems will be assessed using the Movement Disorders Society Unified Parkinson's Disease Rating Scale-III (MDS-UPDRS-III), an 18-item questionnaire that provides an index of motor severity. Represent the Alliance Evaluations Systems Test (Mini-BEST). Participants are asked to stand on one leg, stand on the ground and foam surfaces, and walk while performing different tasks. During the in-person assessments, participants will also wear APDM's Mobility Lab sensors provide detailed spatiotemporal data regarding gait.

Mindfulness Measures. The Revised Cognitive Affective Mindfulness Scale (CAMS-R) has 12 items to assess how participants relate to their thoughts and feelings in relation to attention, awareness, present-focus, and acceptance/nonjudgment in order to achieve an overall mindful state.⁹¹

Psychological Measures. The Hamilton Anxiety Scale (HAM-A) is a 14-item questionnaire to analyze the symptoms and severity of psychic and somatic anxiety. The Hamilton Depression Scale (HAM-D) is a 21-item questionnaire to analyze symptoms such as depressed mood, feelings of guilt, suicidal tendencies, and insomnia. The Penn State Worry Questionnaire is a self-reporting measure with 16 items to index the amount of worry a person experiences. The Parkinson Disease Questionnaire-39 (PDQ-39) is a 39-item self-report survey that provides information on the impact Parkinson disease has on the participant's quality of life.

physical, mental, and social health will be measured using the Neuro-QOL Battery, a self-reported assessment to analyze several domains including anxiety, stigma, depression, social interactions and the ability to do physical tasks while living with a neurological condition.⁹⁶ The Hamilton Anxiety Scale (HAM-A) is a 14-item questionnaire to analyze the symptoms and severity of psychic and somatic anxiety. The Hamilton Depression Scale (HAM-D) is a 21-item questionnaire to analyze symptoms such as depressed mood, feelings of guilt, suicidal tendencies, and insomnia.

Sense of Agency Measure. The Sense of Agency scale is a tool used to measure one's core agency by analyzing the extent to which someone believe to have control over their own body, thoughts, and the environment in order to become more aware of internal and external experiences.⁶⁷

Cognitive Measures. To measure cognition, the NIH Toolbox will be used. Tests include 1) episodic memory with the Picture Sequence Memory Test; 2) working memory via the List Sorting Working Memory Test; 3) the Picture Vocabulary Test and Oral Reading Recognition Test to test language processing; 4) executive functioning via the Dimensional Change Card Sort Test; 5) processing speed using the Pattern Comparison Processing Speed Test and Oral Symbol Digit Test; and 6) the Auditory Verbal Learning Test (Rey) to assess immediate recall.

KEY FEASIBILITY ELEMENTS, EXPECTED OUTCOMES, AND BENCHMARKS

For this first aim, our expected outcomes include demonstrating successful start-up procedures including regulatory approvals, formation of the advisory group, modifications of the MBSR protocol, and standardization of the protocol to use in Aim 2.

For feasibility, we will monitor and track: 1) difficulties that arise during the start-up phase; 2) challenges with formation and meetings with the advisory group; 3) discussions and outcomes during each of the advisory group meetings to ensure objectives are met; 4) challenges that present as a result of modifying the MBSR protocol to focus on walking mediations; 5) comments from the advisory group regarding the outcome measures; and 6) comments regarding clarity of content in the MBSR workbook.

Benchmarks for Aim 1 include: 1) identification and recruitment of the full advisory committee with an initial meeting held within the first three months of the award; 2) complete initial review of all required elements (SOP, Workbook, Literature, Inclusion/Exclusion Criteria, Technology) within five months of initial meeting; and 3) have a final draft of the initial mindfulness-based walking training protocol for rollout in Aim 2 within twelve months of the first advisory committee meeting.

INCLUSION/EXCLUSION CRITERIA

Participants with PD will meet the following inclusion criteria:

- diagnosed by a neurologist with idiopathic PD;
- age 50 and older;
- history of freezing of gait;
- able to provide informed consent;
- able to walk independently with or without an assistive device for at least five minutes; and
- experience fear and/or worry in relation to their FOG.

Care partners of people with PD+FOG will meet the following inclusion criteria:

- able to provide informed consent; and
- able to walk independently with or without an assistive device for at least five minutes.

Participants with PD will be excluded if they have any of the following:

- evidence of dementia (Mini-Mental Status Examination < 24) to ensure understanding of materials;
- are under consideration for deep brain stimulation surgery within the next three months;
- neurologic condition other than PD;
- inability to cooperate with the protocol;

- history of orthopedic or other medical problems that limit ability to participate safely in the practice sessions; or
- language, visual, or hearing barriers to participation.

Care partners of people with PD+FOG will be excluded if they have any of the following:

- evidence of dementia (Mini-Mental Status Examination < 24);
- inability to cooperate with the protocol;
- language, visual, or hearing barriers to participation; or
- history of orthopedic or other medical problems that limit ability to participate safely in the practice sessions.

Aim 2: Refine and standardize the MBWT protocol to ensure feasibility and acceptability through open pilot testing. Twelve people with PD+FOG will participate in the open pilot MBWT program designed in Aim 1. After this open pilot the protocol will be modified based on participant feedback, safety, and satisfaction. Feasibility elements include meeting benchmarks for: recruitment and randomization; retention and satisfaction; delivery of the intervention; participant adherence using technology; evaluating clarity and burden of outcome assessments; and monitoring adverse events.

RATIONALE

Open piloting the MBWT will provide a better standardized MBWT intervention for use in Aim 3. We will be able to monitor the group of participants (n = 12) who receive the MBWT intervention and receive their feedback as well as input from the mindfulness instructors on how to ensure this intervention is prepared for the randomized controlled pilot in Aim 3 and for potential future effectiveness trials.

DESIGN

The new twelve-week MBWT group intervention will be tested in this aim, with modifications of the MBWT program and protocol from the advisory team.

After the participants are deemed eligible via the phone screen, they will be scheduled for their first evaluation (Time 1). Participants will then attend the pre-program orientation session, followed by the twelve-week MBWT program. There will also be a half-day retreat around week nine. Participants will be encouraged to attend all classes in-person in our lab space. However, in case of illness or other circumstances that prevent in-person attendance, the mindfulness instructor and research team member may speak to the participant to see if participating via a video conference platform is feasible, and if the participant is willing and able to do so. Participants will then be asked to complete the post-program evaluation (Time 2) and be encouraged to continue practicing mindfulness on their own, record practice time, and journal their usual care regimes during a second fourteen-week period (the fourteen weeks is to match the time they were in the intervention (pre-program orientation + twelve-week program + half-day retreat). They will then return for a follow-up evaluation (Time 3). There is not any standardized treatment for FOG, thus having participants record their usual care (i.e., health care visits and changes in medications) will provide information for future comparator conditions.

EXPECTED OUTCOMES AND BENCHMARKS - STATISTICAL ANALYSIS PLAN FOR FEASIBILITY STUDY

In addition to having a standardized version of the MBWT intervention and protocol by the end of year two to use in Aim 3, our feasibility aims and benchmarks include:

Ability to recruit our target sample. We estimate screening approximately 70 participants by phone to find 12 participants who meet inclusion criteria and agree to participate. These 12 participants will participate in the preprogram orientation. This anticipated screening rate of 35% is based on our recent interventions. We anticipate two people will decide not to participate after attending the pre-program orientation or Time 1 evaluation, leaving ten participants. We will track reasons for not continuing during the phone screens. *Benchmark:* (1) Recruit one person for every eight screened. (2) Recruitment of 12 participants.

Retention of participants and satisfaction with the intervention. We will collect data on why classes are missed and reasons for drop-outs, if any. Make up classes may need to be scheduled. The Session Evaluation form will provide data for the acceptability and satisfaction of each session. The CSQ will provide acceptability and satisfaction data on the program as a whole. Modifications to the protocol will be informed by these two measures as well as open-ended questions and exit interviews. *Benchmarks:* (3) Attendance and retention of participants, defined as at least 80% participants attending 80% of the sessions; (4) Session satisfaction defined as a minimum average rating of >0.5 on the Session Evaluation Form; and (5) Program satisfaction as a minimum average rating of >1.5 on Client Satisfaction Questionnaire (CSQ).

Participant adherence. Adherence for home practice will be monitored using a tablet (iPad mini) that will prompt the participants daily. The prompts will ask how many minutes they practiced mindfulness today. *Benchmark:* (6) Home practice adherence, at least 70% of participants will complete at least 70% of the daily home assignments during the active intervention period. Number of home practice hours is 20 hours over the course of the mindfulness intervention. (7) Maintenance of practice, at least 50% of participants will report continued engagement in mindfulness practices during the fourteen-week follow-up period.

INCLUSION/EXCLUSION CRITERIA

Participants with PD will meet the following inclusion criteria:

- diagnosed by a neurologist with idiopathic PD;
- age 50 and older;
- a score on the Hoehn & Yahr (H&Y) scale between I-IV;
- history of freezing of gait;
- able to provide informed consent;
- able to walk independently with or without an assistive device for at least five minutes;
- experience fear of falling, frustration, irritation, anxiety, and/or worry in relation to their FOG; and
- stable medication regimen for one month prior to enrollment.

Participants with PD will be excluded if they have any of the following:

- evidence of dementia (Montreal Cognitive Assessment-T < 13) to ensure understanding of materials;
- are under consideration for deep brain stimulation surgery within the next six months or have had DBS surgery within the past six months;
- major depression disorder or post-traumatic stress disorder without permission from health provider to participate;
- neurologic condition other than PD;
- inability to cooperate with the protocol;
- language, visual, or hearing barriers to participation; or
- history of orthopedic or other medical problems that limit ability to participate safely in the intervention.

DATA MANAGEMENT AND POWER ANALYSIS

Data management resources will include developing forms to use for the feasibility aims and entering data into REDCap. [name] has experience with development of REDCap databases for multiple studies, enforcing standard operating procedures, and data monitoring. She has excellent methods for reducing the potential for data errors through smart design of measures and data entry procedures. As this is a feasibility study, a formal power analysis was not conducted. We have adopted statistically efficient designs that control for baseline status (Aims 2 and 3) and selected measures that are reliable and valid among people with PD. We elaborate on this choice in the Statistical Design and Power document. We have a target sample size of 12 people per group (allowing for attrition to n = 10) based on previous studies delivering the mindfulness intervention, discussion with the mindfulness instructors, recommendations in the MBSR standard operating procedures, as well as our knowledge of delivering group-based interventions for people living with PD.

STUDY TIMELINE

Study Milestones	Year 1	Year 2	Year 3
Obtain IRB Approval	X		
Recruit 3-5 Participants to form Advisory Group	X		

Advisory Group Committee Meetings	X		
Finalize Study Procedures/MBWT Protocol	X		
Obtain IRB Approvals on updated Protocol	X		
Aim 2: Participant Recruitment for Wave 1 and 2	X		
Aim 2: Participant Assessments		X	
Aim 2: MBWT Intervention Wave 1 and 2		X	
Aim 2: MBWT Modifications after Wave 1 and 2		X	
Aim 3: Participant Recruitment (MBWT & UC)		X	
Aim 3: Participant Assessments (MBWT & UC)			X
Aim 3: MBWT Intervention and UC			X
Aim 3: MBWT Modifications			X
Feasibility Reports			X
Dissemination via Manuscript Submission			X
Submission of Subsequent Grant Application			X

Abbreviations: MBWT, Mindfulness Based Walking Therapy; UC, Usual Care

STUDY TIMELINE JUSTIFICATION

The first year of the study will be devoted to obtaining IRB approval, forming the advisory committee, and creating the first draft of a MBWT program by modifying the standard MBSR protocol to focus more specifically on walking (Aim 1). In the second year, we will conduct the open pilot study (Aim 2), allowing time between waves to evaluate results and make adjustments to the MBWT intervention after each iteration. The final year will be devoted to piloting of the finalized MBWT intervention and comparing it to usual care in a randomized controlled pilot study (Aim 3). We will utilize results obtained to inform future effectiveness trials and mechanistic studies and plan to submit a grant to support the next steps in this line of research by the end of the third year.

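### Does the 35% screening rate need correcting, given that 12 recruits from about 70 phone screens is 17%?

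*Combined protocol and SAP*

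**What the plan says.** The figure stands in Aim 2, under Expected Outcomes and Benchmarks – Statistical Analysis Plan for Feasibility Study, in the paragraph on ability to recruit the target sample. That paragraph opens with the workload: "We estimate screening approximately 70 participants by phone to find 12 participants who meet inclusion criteria and agree to participate". After saying that these 12 go on to the orientation, it continues: "This anticipated screening rate of 35% is based on our recent interventions". It then allows for early loss: "We anticipate two people will decide not to participate after attending the pre-program orientation or Time 1 evaluation, leaving ten participants".

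The paragraph ends with two benchmarks: (1) "Recruit one person for every eight screened" and (2) "Recruitment of 12 participants".

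Three other places bear on the point:

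- The opening of Aim 2 names recruitment among the things to be judged ("Feasibility elements include meeting benchmarks for: recruitment and randomization") and puts the open pilot at twelve people.
- The Aim 2 Design section makes eligibility at the phone screen a step of its own, before the Time 1 evaluation.
- Data Management and Power Analysis gives a target of 12 per group, falling to 10 with attrition, and says no formal power analysis was done. The Study Timeline lists Aim 2 recruitment and intervention for two waves.

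**The concern.** The sentence with the 35% begins by pointing back, and the only screening quantities before it are 70 and 12. A reader therefore takes 35% to be recruits divided by screens, and 12 of 70 is nowhere near that. The numerator and denominator are not stated here or anywhere else in the document.

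If the 35% were used, this would matter. Recruitment is a named feasibility element, and 35% is the only historical rate offered in its support. A team that recruits 35% of those it screens needs about half as many calls as one that recruits 17%. Anyone comparing the observed rate with the expected one in the feasibility report would also not know which figure to use.

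**Working it through.** **Inputs.** All come from the recruitment paragraph of Aim 2 unless noted: screens, about 70; people found, 12; stated rate, 35%; remaining after two early losses, 10; benchmark (1), 1 in 8; benchmark (2), 12. The Study Timeline gives two waves for Aim 2. Reading the approximate 70 as 60 to 80 is my assumption.

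**1. Can 35% be reproduced as recruits divided by screens?**

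- 12/70 = 17.1%, about 1 in 5.8 (70/12 = 5.83)
- 12/60 = 20.0% and 12/80 = 15.0%
- 10/70 = 14.3%, counting only those expected to remain
- 0.35/0.171 = 2.0, so the stated rate is about twice the implied one; rounding of 70 does not explain this

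Taken the other way, 35% of 70 is 24.5 recruits, and 12 recruits at 35% need 12/0.35 = 34.3, that is 35 screens. The figure is not reproduced on this reading.

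**2. Readings on which 35% could be right**

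- *Share eligible at the phone screen.* 0.35 × 70 = 24.5 eligible, of whom 12/24.5 = 49% must agree. For 60 screens this is 12/21 = 57%; for 80 it is 12/28 = 43%. The 12 are described as people "to find 12 participants who meet inclusion criteria and agree to participate" needs for its count, that is, both eligible and willing, so two steps do lie between 70 and 12. No agreement rate is given, so the documents neither support nor exclude this reading.
- *Two waves of 12.* 24/70 = 34.3%, and 24/0.35 = 68.6, which rounds to about 70. This fits 70 and 35% together without a further rate. Against it, Aim 2 gives its total as twelve people, and benchmark (2) says 12; two waves could share those 12.

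The documents do not settle which reading was meant, or whether the figure is simply a slip.

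**3. What uses the 35%?**

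| Item | Stated as | Depends on 35%? |
|---|---|---|
| Benchmark (1) | 1 recruit per 8 screened, 12.5% | No |
| Benchmark (2) | 12 recruited | No |
| Screening workload | about 70 calls | Not stated to be derived from it |
| Sample size | 12, falling to 10; no formal power analysis; based on earlier studies, instructors' advice and experience with groups | No |
| Benchmarks (3) to (7) | attendance, satisfaction, home practice, maintenance | No |

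**4. Can the recruitment benchmarks be judged without it?** Benchmark (1) needs the number screened and the number recruited; benchmark (2) needs only the latter. Meeting both means at least 12 recruits, with no more than 12 × 8 = 96 screens if exactly 12 are recruited. The planned 12 from 70 is 17.1%, which passes 12.5% and meets 12. A recruit rate of exactly 1 in 8 would give 70/8 = 8.75 people from 70 screens, short of 12. That is no contradiction: benchmark (1) is a floor on efficiency, benchmark (2) is a count, and a minimum may lie below the expected yield.

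**The case for a change.** The best case for a change is that it would cost one sentence, and that a feasibility plan should state its one historical rate so that others can use it. As printed, earlier experience might support 12 from 35 calls or 12 from 70, a twofold difference in effort. Even on the eligibility reading, a reader cannot get from 35% to 12 of 70 without a second rate that is not given.

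There is also a sharper form. If 35% and 70 were worked out for two waves of 12, the figure out of place is the 12, and then the sample size and benchmark (2) would be in question, not just a label.

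The first part stands as a comment on wording: the term is undefined, and 35% is not 12/70. It does not reach the plan, because the number of calls to expect is stated directly and the pass marks do not refer to the rate.

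The sharper form rests on an inference. The closeness of 24/70 to 35% is suggestive, but 24 appears nowhere as an Aim 2 total, whereas 12 appears in the aim statement, its rationale, the recruitment paragraph and benchmark (2). A numerical near-match does not outweigh four consistent statements. It is a reason not to overwrite 35% with 17% on the assumption that 35% must be the error.

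**Conclusion.** The observation is correct and the consequence is nil. The 35% is undefined and is about twice the 17.1% that 12 of 70 gives (15% to 20% if the approximate 70 means 80 to 60, which is my assumption). It may be an unlabelled eligibility share, a two-wave figure or a clerical slip, and the documents cannot decide between them.

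No change to the plan follows. The rate feeds no benchmark, sample size, threshold or analysis, and the text does not say that 70 was derived from it. An analyst reporting feasibility would tabulate the numbers screened, eligible, agreeing and recruited, then apply the one-in-eight and 12-person benchmarks as written, and would reach the same conclusion whatever the 35% was meant to be.

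This rests on taking 12 as the Aim 2 total, as the aim, its rationale and benchmark (2) all state. If the authors tidy the sentence, they should say what the rate counts and whether 12 covers both waves before altering any number.

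### The daily adherence prompt, as described, does not separate home practice from class or retreat practice, so supervised minutes can be counted toward benchmark (6)

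*Combined protocol and SAP*

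**What the plan says.** The relevant text is under Aim 2, Expected Outcomes and Benchmarks (the feasibility SAP), paragraph on participant adherence. The purpose of the tablet is stated first: "Adherence for home practice will be monitored using a tablet (iPad mini) that will prompt the participants daily". The content of the item follows: "The prompts will ask how many minutes they practiced mindfulness today". Benchmark (6) then requires that "at least 70% of participants will complete at least 70% of the daily home assignments during the active intervention period". A further sentence adds: "Number of home practice hours is 20 hours over the course of the mindfulness intervention".

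The Aim 2 Design section sets the supervised component: "Participants will then attend the pre-program orientation session, followed by the twelve-week MBWT program", and "There will also be a half-day retreat around week nine". It allows video attendance when a participant cannot come in person, and the retention paragraph allows make-up classes.

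For standard MBSR, Aim 1 (Structure and Methods) reports class time and home time as separate totals: "The total in-class contact is 30 hours and total home assignments is a minimum of 42 hours".

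**The concern.** The tablet is there to measure home practice, yet the item as described asks about the whole day. It is issued daily, so it also appears on class days and on the retreat day. A participant who meditated in a session that day and answers literally will include those minutes. The plan gives no instruction to leave them out, no second item and no rule for removing session days.

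Attendance already has its own criterion, benchmark (3). Benchmark (6) adds information only if it measures something else. If supervised minutes enter it, it partly measures attendance again, and always in the direction that favours the program. Aim 2 exists to refine the intervention before the randomized pilot in Aim 3, so an inflated figure could hide a weak home component at the stage meant to find it. The same minutes would overstate home dose in any descriptive use. Benchmark (7) is not affected, because no classes are scheduled during follow-up.

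**Working it through.** **Inputs from the documents.** Twelve-week program; one half-day retreat; 70% threshold within participant; 20 hours of home practice. A retreat length of 3.5 h is anticipated in Aim 1. Standard MBSR classes last 2.5 h.

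**Assumptions.** One class per week, so 12 class days. MBWT class length is not given; 0.75 to 2.5 h is used. The share of session time that a participant would log as practice is not given either and is left to vary.

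**The plan's own figure.** The 20 hours comes without minutes per day or a derivation, so it cannot be reproduced. Spread over 12 × 7 = 84 days, it is 20 × 60 / 84 = 14.3 minutes a day.

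**Reading 1: the 70% applies to days (one assignment per day).**
- Days needed: 0.70 × 84 = 58.8, so 59.
- Session days that could be credited: 12 + 1 = 13. A make-up class replaces a missed one and does not raise this.
- Home days then needed: 59 − 13 = 46, which is 46/84 = 54.8% of all days, or 46/71 = 64.8% of the 71 non-session days.
- With session days removed from both sides, the requirement would be 0.70 × 71 = 49.7, so 50 home days. Against that standard the leniency is 50 − 46 = 4 days.
- A participant who attends everything and never practises at home: 13/84 = 15.5%, far below 70%.

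**Reading 2: the 70% applies to the 20 hours.**
- Threshold: 0.70 × 20 = 14 h.
- Supervised hours = (12 × class length + 3.5) × attendance. The last two columns give 14 h divided by those hours, which is the share of session time that must be logged to reach 14 h with no home practice.

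| Class length | Hours, full attendance | Hours, 80% attendance | Share needed, full | Share needed, 80% |
|---|---|---|---|---|
| 0.75 h | 12.5 | 10.0 | not reached | not reached |
| 1 h | 15.5 | 12.4 | 90% | not reached |
| 1.5 h | 21.5 | 17.2 | 65% | 81% |
| 2 h | 27.5 | 22.0 | 51% | 64% |
| 2.5 h | 33.5 | 26.8 | 42% | 52% |

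- Break-even class length if all session time is logged: (14 − 3.5)/12 = 0.875 h at full attendance, and (14/0.8 − 3.5)/12 = 1.17 h at 80%.
- With a lower share the effect is partial. At 2.5 h classes, full attendance and a quarter of the time logged, sessions supply 0.25 × 33.5 = 8.4 h and 5.6 h of home practice is still required.

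No probability of passing the benchmark is given. It would need an assumed distribution of home practice and an assumed proportion of participants who include class minutes, and the documents supply neither.

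**The case against.** The strongest reply is context. The sentence just before the item says the tool is for home practice, the benchmark is labelled as home practice adherence, and it is scored on home assignments. The item is reported in indirect speech; the screen text and participant instructions are not shown and may well be narrower. This stands in part. A reader might infer that the plan counts class and retreat minutes as home practice, and the documents do not support that: no sentence says so. What remains is an ambiguity. A stated purpose does not filter the data, because participants answer the prompt put to them.

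A reader might also infer that someone who only attends class could meet benchmark (6) with almost no home practice. On the benchmark's literal wording this fails, as the 15.5% figure shows. It becomes possible only under the hours reading, which attaches the 70% to a total that the plan states in a separate sentence, and then only for some combinations of class length and logged share. The hours reading cannot be dismissed, since the item collects minutes and the 20 hours sits within the benchmark, but the plan does not state it.

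Finally, this is a 12-person open pilot. Protocol changes also draw on session evaluations, the satisfaction questionnaire, open-ended questions and exit interviews, with adjustment planned between waves. It would be speculative to say that this benchmark alone would carry the home component unchanged into Aim 3.

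**Conclusion.** The point holds as a measurement ambiguity with a known direction. As described, the prompt cannot isolate home practice, and any error from this source raises apparent home adherence.

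The size depends on a scoring rule that the plan leaves undefined. By days, the effect is modest: the bar on non-session days drops from 70% to about 65%, given weekly classes, one retreat day and every session day credited. By hours, it ranges from partial help to the whole 14 h threshold, and that range rests on assumed class length, attendance and logged share. This is an inexpensive improvement to make, and it does not show that the benchmark is invalid.

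**What to change.** Reword the prompt, for example: How many minutes did you practise mindfulness today outside class and the retreat, whether you attended in person or by video? Make-up sessions should be treated as class.

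Add to benchmark (6) that only these minutes count, and state whether the 70% applies to days, assignments or hours, with its denominator.

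If the tablet item can no longer be changed, use attendance records to exclude each participant's session dates (class, make-up and retreat) from both numerator and denominator. With full attendance that means at least 50 of 71 days on the day reading. On an hours reading the 20 h target would need matching proration.

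The cost is one phrase in the prompt and one or two sentences in the plan, with no added visits, staff or participants. Observed adherence may come out lower, and the fallback discards genuine home practice done on session days.
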